**Table 4: Phase 1b Study Dose Level and Schedule**

DSP-7888 Dosing Emulsion Dose Level	DSP-7888 Dosing Emulsion Dose and Schedule
DSP-7888 Dosing Emulsion Dose Level I	Nivolumab Arm (Arm 1): 10.5 mg weekly for 4 weeks for induction phase, then every 2 weeks for maintenance phase Pembrolizumab Arm (Arm 2): 10.5 mg weekly for 3 weeks for induction phase, then every 3 weeks for maintenance phase
DSP-7888 Dosing Emulsion Dose Level II	Nivolumab Arm (Arm 1): 3.5 mg weekly for 4 weeks for induction phase, then every 2 weeks for maintenance phase Pembrolizumab Arm (Arm 2): 3.5 mg weekly for 3 weeks for induction phase, then every 3 weeks for maintenance phase
DSP-7888 Dosing Emulsion Dose Level III	Nivolumab Arm (Arm 1): 1.75 mg weekly for 4 weeks for induction phase, then every 2 weeks for maintenance phase Pembrolizumab Arm (Arm 2): 1.75 mg weekly for 3 weeks for induction phase, then every 3 weeks for maintenance phase

**Table 5: PD-1 Inhibitor Dose**

PD1 Inhibitor	Dose and Schedule
Nivolumab	In Arm 1, 240 mg administered intravenously (IV) over 30 minutes ( $\pm 5$ )* every 14 days (2 weeks/cycle) starting from Day 1 of Cycle 3 (Day 29), then maintenance phase (after Cycle 3).
Pembrolizumab	In Arm 2, 200 mg/8 mL administered through IV infusion over 30 ( $\pm 5$ ) minutes every 21 days (3 weeks) starting from Day 1 of Cycle 2 (Day 22), then maintenance phase (after Cycle 2).

\*The administration time change from 60 to 30 minutes is based on the updated dosage and administration guidance of the new nivolumab product label released in July 2018.

**6.3.2. Phase 2 (Dose-Expansion Part)**

Patients will have access to study treatment as long as they are benefiting from study treatment or have received up to a total of 35 treatment cycles (approximately 105 weeks). Patients may continue the study treatment beyond 35 treatment cycles if the patient is experiencing clinical benefit, after documented discussion with the Sponsor.

DSP-7888 Dosing Emulsion and pembrolizumab will be administered at the recommended dose level from the Phase 1 part of the study, following the same schedule as listed in [Table 6](#).

**Table 6: Phase 2 Study Dosing Schedule**

Investigational Product	Frequency	Dosage	Route of Administration
DSP-7888 Dosing Emulsion	Q1W for first 3 weeks Q3W post 3 weeks	10.5mg	Intradermal injection (ID)
Pembrolizumab	Q3W, starting from Day 1 of Cycle 2 (Day 22)	Solution for infusion 200mg/8mL	IV infusion

#### 6.4. Dose-limiting Toxicities (Phase 1b Dose Search Part Only)

A dose-limiting toxicity (DLT) is defined by the occurrence of 1 of the toxicities defined below, occurring during the first 28 days of Arm 1 (DSP-7888 Dosing Emulsion induction phase in combination with nivolumab; Arm 1) and the first 42 days of Arm 2 (DSP-7888 Dosing Emulsion induction phase in combination with pembrolizumab; Arm 2).

Evaluable patients are defined per Dose-Determining Set (DDS), as defined in [Section 12.1.2.3](#). Patients who discontinue before meeting the DDS criteria may be replaced to fully evaluate a given dose level. The criteria for the determination of DLT will apply to a given administration schedule independently.

No inpatient dose escalation/de-escalation is allowed during the DLT evaluation period.

**The following treatment-related AEs will be considered a DLT:**

##### **Non-hematologic**

- Any treatment-related Grade 3 or higher non-hematologic clinical (non-laboratory) AE, with the following exceptions:
  - Grade 3 nausea/vomiting or Grade 4 vomiting that resolves to Grade 1 or 2 in 72 hours or less with appropriate supportive care
  - Grade 3 or 4 diarrhea that resolves to Grade 1 or 2 in 72 hours or less with appropriate supportive care
  - Grade 3 fatigue lasting <5 days
  - Grade 3 hypertension that can be controlled with medical therapy within 7 days
- Any treatment-related Grade 3 or higher non-hematologic laboratory abnormality if:
  - Medical intervention is required to treat the patient, or
  - The abnormality leads to hospitalization, or
  - The abnormality persists for  $\geq 7$  days

##### **Hematologic**

- Any treatment-related hematologic toxicity specifically defined as:
  - Thrombocytopenia Grade 4 or higher, or Grade 3 associated with bleeding
  - Neutropenia Grade 4 for  $\geq 7$  days, or Grade 3 or 4 associated with infection or febrile neutropenia
  - Anemia Grade 4, or Grade 3 or 4 requiring blood transfusion

##### **Immune-related**

- Grade 3 or higher CTCAE v. 4.03 immune system disorder-related adverse reactions that persist as Grade 3 for >14 days, despite appropriate treatment, except for allergic reactions and autoimmune reaction
- Any Grade 3 or higher allergic reaction

- Any Grade 2 or higher autoimmune reaction with the following exceptions:
  - Grade 2 elevation of transaminases/hepatitis that recovers to Grade 0 or 1 within 10 days (for patients with liver metastases, elevation of transaminases due to hepatitis that recovers to baseline within 10 days)
  - Grade 2 hypothyroidism that recovers to Grade 0 or 1 within 7 days without steroids
  - Grade 2 diarrhea/colitis that spontaneously recovers to Grade 0 or 1 within 7 days with supportive care but without steroids
  - Grade 2 immune-related rash/dermatitis
- Any treatment-related Grade 4 ISR or Grade 3 ISR that requires hospitalization.

Any patient who experiences a DLT should be permanently removed from study treatment and should not be replaced.

Note that DSP-7888 Dosing Emulsion dosing has been managed with dose interruptions and/or adjustments for ISRs/AEs. Therefore, a DSP-7888 Dosing Emulsion dose interruption/delay for an AE related to an ISR that does not meet a DLT definition, as described above, will be considered a non-DLT modification. Non-DLT dose modifications will not be considered in determining the recommended dose for DSP-7888 Dosing Emulsion; however, they will be considered in determining further management of the DSP-7888 Dosing Emulsion dosing schedule in the expansion part, in combination with the selected PD-1 inhibitor.

### **6.5. Defining Recommended Dose of DSP-7888 Dosing Emulsion with Nivolumab or Pembrolizumab (Only Phase 1b Dose Search Part)**

The determination of the recommended dose of DSP-7888 Dosing Emulsion in combination with nivolumab or pembrolizumab will be based on the criteria defined herein.

Initially, 6 patients will be enrolled into each of the arms according to a rolling 6 study design at the DSP-7888 Dosing Emulsion Dose Level I (of 10.5 mg weekly) in combination with either nivolumab 240 mg (every 2 weeks; Arm 1) or pembrolizumab 200 mg (every 3 weeks; Arm 2).

The recommended dose of DSP-7888 Dosing Emulsion in combination with a given PD-1 inhibitor agent will be determined in each study arm. Dose adjustments will proceed independently in each study arm. The recommended dose of DSP-7888 Dosing Emulsion must be less than or equal to a dose level at which 1 out of 6 patients enrolled experience a DLT (see definition of a DLT in [Section 6.4](#)). A dose level is eligible for consideration as the recommended dose if 0 or 1 of 6 patients enrolled experience a DLT at that dose level.

Criteria for determining whether a given dose level is eligible to be considered a recommended dose of DSP-7888 Dosing Emulsion are based on the number of patients with DLTs out of the total number of DLT-eligible patients in a given cohort. The criteria are as specified below:

- If 0 or 1 of 6 patients at the starting dose level experience a DLT, the dose level is eligible for consideration as the recommended dose of DSP-7888 Dosing Emulsion
- If 2 or more of 6 patients at a given dose level experience a DLT, the dose will be decreased. Further enrollment will be at the lower dose level. If 0 or 1 of 6 patients at

the lower dose level experience a DLT, the dose level is eligible for consideration as the recommended dose of DSP-7888 Dosing Emulsion

The determination of the recommended dose of DSP-7888 Dosing Emulsion in a given study arm also will be based on overall tolerability, including a review of persistent Grade 2 AEs and a review of AEs occurring beyond the first 2 cycles.

The safety and tolerability of DSP-7888 Dosing Emulsion in combination with immunotherapy PD-1 inhibitors will be assessed for the duration of study treatment and 30 days follow-up.

## 6.6. Safety Review Committee

The Safety Review Committee (SRC) for Phase 1b dose-escalation will be chaired by the [REDACTED]. The SRC will include the Principal Investigator (or delegate) from each of the investigational sites. The SRC will also include a representative from [REDACTED] PV (or designee), an [REDACTED] Biostatistician (or designee), and a representative from [REDACTED] Clinical Research. The SRC will review the safety and tolerability of DSP-7888 Dosing Emulsion in combination with nivolumab and pembrolizumab in each cohort to decide the next dose level to be tested. In addition, all immune-related AEs occurring in Arm 1 and Arm 2 will be evaluated throughout the conduct of this study. The SRC's review and assessment will include all available safety data from each cohort, together with available PD data. The SRC's review will also include an assessment of all cases, individually and in aggregate, for those patients who meet the criteria for DLT in order to determine the clinical significance and basis for their inclusion or exclusion in the decision for dose change.

The SRC will review and agree on the recommended maximum tolerated dose prior to enrolling patients in the dose-expansion part. In the dose-search cohort (Phase 1b), the stopping rule will follow the rule of the 3+3 design. All decisions made by the SRC will be documented and provided in writing to the investigators before dosing any new patients.

In Phase 2 of the study, the Sponsor will decide the necessity for a study suspension, protocol amendment, continuation of enrollment, or termination of the study if the following criteria are met:

- Any cases of death (other than death related to progressive disease) that occur from the start of treatment with DSP-7888 Dosing Emulsion and up to 30 days from the last DSP-7888 Dosing Emulsion administration, and deemed by the Sponsor to be related to any of the study's drugs
- If the percentage of patients in this study presenting with drug-related (assessed by Sponsor) Grade 4 or higher AE within a particular medical concept (eg, hypersensitivity) is higher than that reported in patients treated with DSP-7888 Dosing Emulsion within the clinical program, and as reported in the literature

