#### **6.1.4.5. Follow-up Period**

The follow-up period will begin once a patient has discontinued study treatment. Follow-up period includes disease assessment follow-up (for patients who discontinue study treatment for a reason other than iCPD per iRECIST) and survival follow-up.

Patients who discontinue study treatment without experiencing iCPD will continue to undergo tumor assessment and evaluation of CA-125 (Phase 2), according to the SOA until up to 24 months after last dose of study drug, the start of new anticancer therapy, iCPD per iRECIST, death, loss to follow-up, withdrawal of consent, or the end of the study, whichever occurs first.

Patients who discontinue study treatment when experiencing iCPD per iRECIST with study drug, or patients who discontinue study treatment without experiencing iCPD per iRECIST, but who experience iCPD per iRECIST or start new anticancer therapy during disease follow-up will be assessed for survival and new anticancer treatment status per the SOA, until up to 24 months

after the last dose of study drug, death, withdrawal of consent, loss to follow-up, or end of the study, whichever occurs first.

[figure not shown]
The safety and tolerability of DSP-7888 Dosing Emulsion in combination with immunotherapy PD-1 inhibitors will be assessed for the duration of study treatment and follow-up (see [Table 7](#), [Table 8](#), and [Table 9](#) for the respective SOAs).

All AEs will be collected and recorded for each patient from the date of signing the main ICF for the study until 30 days after last study drug administration. Any pregnancies that occur within 180 days after last study drug administration are to be captured. An AE will be followed until it is either resolved, has returned to baseline, or is determined to be a stable or chronic condition (see [Table 7](#), [Table 8](#), and [Table 9](#)).

[figure not shown]

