### **8.3. Dose Modification**

Any study treatment may be interrupted at any time for any grade toxicity considered intolerable by the patient, based on the investigator's and patient's judgment.

In the case of any patient who has missed 4 or more consecutive doses of either study drug, that study drug should be permanently discontinued, but the patient may continue on the other nonmissed study drug. If the patient is experiencing clinical benefit and, in the opinion of the investigator it is in the patient's best interest to remain on study, the patient may continue treatment on a case-by-case basis, after documented discussion with the Sponsor.

Dose modification by treatment is described in the following sections.

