##### **8.3.2.2. Dose Interruption**

DSP-7888 Dosing Emulsion must be interrupted for any CTCAE (v.4.03) Grade 3 or 4 AE that the investigator considers to be related to DSP-7888 Dosing Emulsion. If toxicity is resolved to Grade 1 or less/baseline, the patient may restart treatment with DSP-7888 Dosing Emulsion but with a dose level reduction.

EXCEPTION: Because more serious ISRs (eg, Grade 3) may take longer to resolve due to the tissue injury, resolution to Grade 2 only is required for restart of treatment with DSP-7888 Dosing Emulsion. However, no dose reduction is required for following cases:

- Grade 3 or 4 hematologic laboratory abnormality which resolves to Grade 1 or less within 7 days without supportive care (blood transfusion or G-CSF agents)
- Grade 3 or 4 non-hematologic laboratory abnormality which resolves to Grade 1 or less within 7 days
- Grade 3 ISR that does not require hospitalization; patients may continue on the study treatment per investigator's judgment
- Grade 3 fatigue, fever, malaise, edema per CTCAE (v.4.03), which resolves to Grade 1 or less within 5 days, with appropriate supportive care
- Grade 3 nausea, vomiting, diarrhea per CTCAE (v.4.03), which resolves within 3 days, with appropriate supportive care

Before discontinuation of dosing for any of the above reasons, a conversation with the Medical Monitor may be applicable.

If toxicity is not resolved to Grade 1 or less (or Grade 2 or less in the case of ISRs, as described above) within 4 consecutive missing doses and, in the opinion of the investigator, the patient is clinically stable and receiving benefit from study drug, the patient may restart treatment with DSP-7888 Dosing Emulsion at a reduced dose on a case-by-case basis, only after consultation with the Sponsor.

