#### 11.1.2.2.3. Adverse Event Severity

The severity of AEs will be assessed according to the National Cancer Institute (NCI) Common Terminology Criteria for Adverse Events (CTCAE), v4.03. For events not specifically found in CTCAE, the following definitions will be used to estimate grade of severity:

- Grade 1: Mild; asymptomatic or mild symptoms; clinical or diagnostic observations only; intervention not indicated
- Grade 2: Moderate; minimal, local or noninvasive intervention indicated; limiting age appropriate instrumental activities of daily living (ADL)
- Grade 3: Severe or medically significant but not immediately life-threatening; hospitalization or prolongation of hospitalization indicated; disabling; limiting self-care ADL
- Grade 4: Life-threatening consequences; urgent intervention indicated
- Grade 5: Death related to AE

The term "severe" is often used to describe the intensity (severity) of a specific event (as in mild, moderate, or severe myocardial infarction); the event itself, however, may be of relatively minor medical significance (such as severe nausea). This is not the same as "serious," (outlined in [Section 11.1.2.1.3](#) which is based on patient/event outcome or action criteria usually associated with events that pose a threat to a patient's life or functioning.

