Treatment-related TEAEs are those judged by the investigator to be at least possibly related to the study drugs (DSP7888 and/or CPI) or for which relatedness is recorded as “unknown” by the investigator. Treatment related will include “possible”, “probable” or “definite” causality assessments. Missing relationship will be considered as “Related” to all drugs received by the patient. Similar summaries as noted for all causality TEAEs will be provided for treatment related TEAEs.

Serious Adverse Events and Death

Treatment-emergent SAEs and Treatment-related SAEs will be summarized by MedDRA SOC and PT and maximum CTCAE grade.

TEAE leading to death will be summarized by MedDRA SOC and Preferred Term.

Deaths will be summarized by on study and on treatment (within 30 days of last dose of study medication). The number and percentage of patients who died on study and on treatment, as well as primary cause of death will be summarized. Deaths may also be categorized according to time of occurrence after first dose.

A listing of death data will also be provided and will include all deaths that occurred from the signing of the informed consent to the end of the follow up period. The listing will include primary cause of death and the number of days relative to the administration of first and last dose.

Adverse Events of COVID-19

Preferred Terms corona virus infection and coronavirus test positive will be used to identified COVID-19 positive cases in adverse event.

Injection Site Reaction (ISR)

The predominant adverse effect observed with DSP-7888 is injection site reaction. The Preferred Terms of TEAEs within the High Level Group Term of “Administration Site Reaction” (MedDRA version 20.0) will be used to identify events of injection site reaction.

Below analysis will be provided for ISR:

- ISR by SOC, PT, and maximum CTCAE Grade
- Onset time of first ISR for patients with at least one ISR: Time to onset is analyzed for patients with at least one ISR from the first dose of the DSP-7888 to the first occurrence of ISR regardless of CTCAE grade.
- Onset time of first ISR: Time to first ISR is defined as the time from the first dose of the DSP-7888 to the first occurrence of ISR . For patients with no ISR, the onset time will be censored as data cutoff date,

end of study date, death date, or safety follow-up completion date (end of treatment date + 30 days) whichever is shorter.

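### The Phase 2 death criterion covers deaths related to either drug, but its window closes 30 days after the last DSP-7888 dose even if pembrolizumab continues (minor)

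*Protocol*

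**What the plan says.** Under Protocol 6.6, if either of two criteria is met in Phase 2, "the Sponsor will decide the necessity for a study suspension, protocol amendment, continuation of enrollment, or termination of the study".

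- **First criterion.** Any death not due to progressive disease that the Sponsor deems related to any of the study's drugs, limited to deaths "that occur from the start of treatment with DSP-7888 Dosing Emulsion and up to 30 days from the last DSP-7888 Dosing Emulsion administration".
- **Second criterion.** The percentage of patients "presenting with drug-related (assessed by Sponsor) Grade 4 or higher AE within a particular medical concept (eg, hypersensitivity) is higher than that reported" for DSP-7888 in the clinical program and in the literature. It has no time window. It includes fatal events, because the severity scale in 11.1.2.2.3 lists "Grade 5: Death related to AE".

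Two dosing provisions bear on the first criterion. Section 8.3.2.2 states that "DSP-7888 Dosing Emulsion must be interrupted for any CTCAE (v.4.03) Grade 3 or 4 AE that the investigator considers to be related" to it. Section 8.3 says of a drug with four or more consecutive missed doses "that study drug should be permanently discontinued, but the patient may continue on the other nonmissed study drug".

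Other safety windows run from the last study drug. Adverse events are collected "until 30 days after last study drug administration" (6.1.4.5). SAP 5.4.1 classes a death as "on treatment (within 30 days of last dose of study medication").

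**The concern.** The first criterion judges causality against both drugs but sets its clock by one. If DSP-7888 is held or stopped and pembrolizumab continues, a death related to pembrolizumab, or a late death related to DSP-7888, can occur more than 30 days after the last DSP-7888 dose and not meet the criterion. This can happen while the patient is still receiving pembrolizumab.

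This is the only Phase 2 criterion that any single related death meets automatically. The second criterion could also be met by one death, but only if the resulting percentage exceeds an external rate that the documents do not give. What is at stake is therefore a prespecified obligation to make and record a decision after a related death. No endpoint, sample size or efficacy decision threshold is affected.

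**Working it through.** The plan gives no figure to reproduce. The check compares the windows and then counts days on the dosing schedule.

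**1. Windows side by side**

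| Provision | Window ends |
|---|---|
| Protocol 6.6, Phase 2 death criterion | 30 days after last DSP-7888 |
| Protocol 6.1.4.5, AE collection | 30 days after last study drug |
| Protocol 11.1.2.3.8, deaths reported as SAEs | 30 days after last investigational agent |
| Protocol Table 9, Phase 2 end of treatment | 30 days after last dose, no drug named |
| SAP 5.4.1, on-treatment deaths | 30 days after last study medication |

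Among these Phase 2 provisions, only 6.6 names DSP-7888 alone. The start of its window causes no difficulty, because DSP-7888 begins on Day 1 and pembrolizumab begins the same day (Amendment 4) or on Day 22 (Amendment 5).

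**2. Can pembrolizumab outlast DSP-7888?** Yes. Section 8.3 is general and permits it. Section 6.1.4.4 schedules pembrolizumab every three weeks up to Cycle 35, and 6.1.4.1 allows treatment beyond that after discussion with the Sponsor.

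**3. Day counts.** Inputs: 21-day interval (Table 6) and 30-day window (6.6). Set day 0 at the last DSP-7888 dose, and let pembrolizumab continue on schedule.

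- Day of the k-th missed DSP-7888 dose = 21k.
- Days since the 6.6 window closed, at that dose = 21k − 30.
- Uncovered days if pembrolizumab is last given at that visit = (21k + 30) − 30 = 21k.

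| k missed | Day | 21k − 30 | Uncovered days |
|---|---|---|---|
| 0 | 0 | −30 (open) | 0 |
| 1 | 21 | −9 (open) | 21 |
| 2 | 42 | 12 | 42 |
| 3 | 63 | 33 | 63 |
| 4 | 84 | 54 | 84 |

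At k = 4, the discontinuation threshold in 8.3, the window has already been closed for 54 days. The 84 days are not a cap, since pembrolizumab may continue from there.

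**4. Extreme case within 35 cycles.** The last DSP-7888 dose is on Cycle 1 Day 15, and pembrolizumab is given to Cycle 35 Day 1.

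- Last pembrolizumab: 1 + 34 × 21 = day 715.
- 6.6 window closes: 15 + 30 = day 45.
- Any-drug window closes: 715 + 30 = day 745.
- Uncovered: 745 − 45 = 700 days.

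This is an upper illustration, not an expected value.

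**5. Does the second criterion fill the gap?** One death is 1/20 = 5.0%, 1/40 = 2.5% or 1/60 = 1.7% of Phase 2 at the interim, planned and maximum sizes. Whether any of these exceeds the comparison rate cannot be determined, because the documents give no such rate.

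**The case against.** **The window changes neither information nor authority.** The criterion concerns deaths that the Sponsor has already judged related, so the Sponsor knows of them. SAEs must be reported within 24 hours, and investigator-suspected related SAEs remain reportable after the 30-day period (11.1.2.4.1). The Sponsor may terminate the study at any time (7.3.2). This stands, and it is why the point is minor. What is lost is the mandatory prompt, not detection.

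**The route to pembrolizumab alone is narrow.** Section 7.3.1 lists an AE that precludes DSP-7888, and withdrawal of consent for either drug, as reasons to stop protocol therapy. Section 8.3.2.2 mainly concerns restarting DSP-7888, and a restart moves the window. The express provision for continuing a PD-1 inhibitor alone, in 8.3.1, is for Phase 1b. This reduces the likely number of affected patients, but 8.3 still permits single-drug continuation. For a patient who dies while off DSP-7888, the last dose date is fixed and no restart can move it.

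**A DSP-7888 clock may be deliberate.** Section 11.1.2.2.4 treats the PD-1 inhibitors as comparator or co-suspect drugs, and the Phase 1b schedules (Tables 7 and 8) tie end of treatment to DSP-7888. Those tables do not govern Phase 2, however. Table 6 lists pembrolizumab as an investigational product there, and the criterion itself extends causality to any study drug.

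**The day counts are nominal.** This is correct. Table 9 allows ±7 days from Cycle 5, so a last DSP-7888 dose at +7 and a second missed visit at −7 are 42 − 14 = 28 days apart, with the window still open.

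**Conclusion.** The point holds as a minor fault in the safety rule. As written, the first Phase 2 criterion excludes some deaths that its own causality scope is meant to include. The gap is zero when both drugs stop at the same visit. Otherwise it is nominally 21 days for each three-weekly DSP-7888 dose missed at the end of treatment while pembrolizumab continues.

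This rests on two readings: that 8.3 applies in Phase 2, and that 7.3.1 narrows it without overriding it. The figures are calendar days, not a risk estimate, and the documents do not say how often pembrolizumab is given alone. Confidence in the mismatch is high, but its practical effect on this trial is small because Phase 2 has been terminated.

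**What to change.** In Protocol 6.6, end the first criterion's window at *up to 30 days from the last administration of any study drug (DSP-7888 Dosing Emulsion or pembrolizumab)*. The uncovered time then falls to zero relative to the last dose of either drug, and the rule agrees with 6.1.4.5 and SAP 5.4.1.

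The cost is one clause through the usual amendment and IRB/IEC review. It needs no new data, no change to sample size or decision thresholds, and no change to the CSR. With Phase 2 terminated, the benefit is confined to any patient still on study drug (the documents do not say whether there are any) and to keeping the wording out of a later protocol that reuses this rule.
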